11.11.6. Pharmacodynamic Figures

Pharmacodynamic: Figures					
No.	Population	IDSL / TST ID / Example Shell	Title	Programming Notes	Deliverable [Priority]
¹⁸F-FDG PET/CT semi-quantitative parameters					
2.1.	Safety	EEF_F1	Plot of Individual ¹⁸ F-FDG PET/CT Parameters by ROI	Paginated by Parameter and ROI. Column panel by side. Plot Subject number along X axis and parameter value along Y axis.	SAC
2.2.	Safety	EFF_F2	Mean (+/- SE) of ¹⁸ F-FDG PET/CT Parameters	Paginated by Parameters and ROI. Plot Sides along X axis and Mean along Y axis. Note: If transformation is required then use median +/- IQR	
2.3.	Safety	EFF_F2	Mean (+/- 95% CI) of ¹⁸ F-FDG PET/CT Parameters	Paginated by Parameters and ROI. Plot Side along X axis and Mean along Y axis. Note: If transformation is required then use median +/- IQR	SAC
2.4.	Safety	EFF_F7	Ratio of SUV _{peak} (Left/Right) Assessing Asymmetry in ¹⁸ F-FDG PET/CT Parameter	X-axis: Subject Y-axis: Ratio of SUV _{peak} (left/right) Include reference line at Y=1. Footnote: Ratio of 1 (reference line) represents complete symmetry.	SAC

Pharmacodynamic: Figures					
No.	Population	IDSL / TST ID / Example Shell	Title	Programming Notes	Deliverable [Priority]
¹¹C-MET PET/CT semi-quantitative parameters					
2.5.	Safety	EFF_F1	Plot of Individual ¹¹ C-MET PET/CT Parameters by ROI	Paginated by Parameter and ROI. Column panel by side. Plot Subjects along X axis and parameter value along Y axis. Colour and symbol by subject group.	SAC
2.6.	Safety	EFF_F3	Mean (+/- SE) of ¹¹ C-MET PET/CT Parameters.	Paginated by Parameters and ROI. Panel by sides Plot Groups (HV/pSS) along X axis and parameter value along Y axis. Note: Difference will not be presented for this plot	SAC
2.7.	Safety	EFF_F3	Point estimate and 95% CI for ¹¹ C-MET PET/CT Derived Parameter of Difference in pSS vs. HV	Page by parameter and ROI. When applicable for a given ROI, the analysis will be separated by side. Plot Subject Groups along X axis and SUV along Y axis. Subheading: 'Parameter: [parameter name]' 'ROI: [ROI name]' Footnote: Difference calculated as pSS-HV. Parameters to include: SUVpeak, SUVmax and SUVmean	SAC

Pharmacodynamic: Figures					
No.	Population	IDSL / TST ID / Example Shell	Title	Programming Notes	Deliverable [Priority]
2.8.	Safety	EFF_F6	Posterior Group Means and the Difference in Group Means for ¹¹ C-MET PET/CT Parameter by Region	Paginate by parameter and ROI. Panel by side where appropriate. X-axis- include group (HV pSS) and difference Footnote: Difference calculated as pSS-HV. Parameters to include: SUVpeak, SUVmax and SUVmean	SAC
2.9.	Safety	EFF_F7	Ratio of SUV _{peak} (Left/Right) Assessing Asymmetry in ¹¹ C-MET PET/CT Parameter	X-axis: Subject Y-axis: Ratio of SUVpeak(left/right) Colour and symbol by subject group Include reference line at Y=1. Footnote: Ratio of 1 (reference line) represents complete symmetry.	SAC
Multiparametric MRI quantitative parameters					
2.10.	Safety	EFF_F1	Plot of Individual Multiparametric MRI Parameters by ROI	Paginated by Parameter and ROI. Column Panel by side. Plot Subject along X axis and parameter value along Y axis. Colour and symbol by subject group.	SAC
2.11.	Safety	EFF_F3	Mean (+/- SE) Plot of MRI Parameters	Paginated by Parameters and ROI. Panel by sides Plot Groups (HV/pSS) along X axis and Parameters along Y axis.	SAC

Pharmacodynamic: Figures					
No.	Population	IDSL / TST ID / Example Shell	Title	Programming Notes	Deliverable [Priority]
2.12.	Safety	EFF_F3	Point estimate and 95% CI for Multiparametric MRI Derived Parameter of Difference in pSS vs. HV	
Page by Regions of Interest and MRI parameter (i.e Ktrans, D, f, ADC). When applicable for a given ROI, the analysis will be separated by side (left/right/aggregated). Plot Subject Groups along X axis and parameter along Y axis. Panel by side where appropriate. Subheading: 'Parameter: [parameter name]' 'ROI: [ROI name]' Footnote: Difference calculated as pSS-HV.
	SAC
2.13.	Safety	EFF_F6	Posterior Group Means and the Difference in Group Means for Multiparametric MRI Parameter by Region	
Paginate by parameter and ROI. Panel by side (include left/right/aggregated) where appropriate. X-axis- include group (HV/pSS) and difference Footnote: Difference calculated as pSS-HV. Parameters to include: Ktrans, D, f, ADC. Median will be used for each parameter.
	SAC

Note: Above figures will be produced only if data is available.

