## **9. STATISTICAL CONSIDERATIONS AND DATA ANALYSES**

### **9.1. Hypotheses**

This study is designed to explore the use of  $^{18}\text{F}$ -FDG PET/CT,  $^{11}\text{C}$ -MET PET/CT, and multi-parametric MRI in pSS subjects and/or healthy volunteers. Due to the exploratory nature of this study, there are no formal hypotheses being tested.

For  $^{11}\text{C}$ -MET PET/CT and multi-parametric MRI, summary statistics will be used to interpret each derived parameter. An exploratory comparison of pSS subjects vs healthy volunteers may be performed for each  $^{11}\text{C}$ -MET PET/CT and multi-parametric MRI derived quantitative parameter as data permits, to estimate difference (or ratio if log transformation is needed) with 95% confidence interval.

For  $^{18}\text{F}$ -FDG PET/CT where only pSS subjects will be scanned, summary statistics will be used to present each derived parameter.

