#### **Group B: Primary Sjögren's Syndrome Subjects**

Approximately 8 to 12 pSS subjects will be recruited. Due to anticipated greater variability amongst patients, the variability of the imaging parameters will be assessed after approximately 8 subjects have been recruited, and consequently up to an additional 4 subjects may be recruited.

Following a literature review the following information was obtained for the imaging modalities of interest in the parotid glands in different populations. This historical information can be used in the variability assessment as outlined above.

Imaging modality; Parameter	Healthy Volunteers Mean [SD]	Patients (not pSS) Mean [SD] n	Patients (pSS) Mean [SD] n	Reference
$^{18}\text{F}$ -FDG PET; $\text{SUV}_{\text{max}}$	n/a	1.80 [0.53] n=25	n/a	Basu, 2008
$^{18}\text{F}$ -FDG PET; $\text{SUV}_{\text{max}}$	n/a	2.00 [not stated]	2.75 [0.61] n=32	Cohen, 2013
$^{18}\text{F}$ -FDG PET; SUV	n/a	1.90 [0.68] n=78	n/a	Nakamoto, 2005
$^{11}\text{C}$ -MET PET; $\text{SUV}_{\text{max}}$	6.00 [1.5] n=11	n/a	n/a	Isohashi, 2013
DCE MRI, $K_{\text{trans}}$	0.20 [0.04] n=11	n/a	0.26 [0.05] n=21	Roberts, 2008
SD=Standard Deviation				

Using estimates of parameter (this can be any parameter,  $\text{SUV}_{\text{mean}}$ , SUV,  $K_{\text{trans}}$ ) variability, the precision of these estimates calculated as half width of a 95% confidence interval for the mean and expressed as distance from mean to limits, for 4, 8 and 12 subjects has been calculated (Table 5).

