Planned Analyses	
 • Interim analyses are detailed within Section 3.1 where applicable. • All decisions regarding final analysis, as defined in this RAP document, will be made prior to Database Freeze of the study data.
Analysis Populations	
 • The Screened Population (Comprises of subjects who sign the Informed Consent) will be used for the evaluation of Screen Failure subjects • The Safety Population (Comprised of all subjects who receive/undergo any Visit 1 procedure). will be used for the evaluation of Study Population and Safety. • The Pharmacokinetic (PK) Population (Comprised of subjects in the ‘Safety’ population for whom radio-pharmacokinetic sample was obtained and analysed) will be used for the evaluation of Pharmacokinetic Analysis.
Hypothesis	
 • There are no formal hypotheses being tested in the study; instead an estimation and inference approach will be adopted to evaluate the objectives.
Primary Analyses	
 • Descriptive statistics and graphical displays, if appropriate, will be presented for all FDG PET/CT derived parameters across the regions of interest (ROI) for all pSS subjects and for all ¹¹C-MET PET/CT and MRI derived parameters across the ROI for all healthy volunteers and pSS subjects. • An exploratory comparison of pSS subjects vs healthy volunteers may be performed for each ¹¹C-MET PET/CT and MRI derived quantitative parameter as data permit, to estimate a difference (or ratio if log transformation is needed) with 95% confidence interval.
Secondary Analyses	
 • Descriptive statistics and graphical displays, if appropriate, will also be presented for all derived parameters from dynamic PET imaging and PK analyses. • If data permits, statistical analyses of ¹¹C-MET PET radio-PK modelling indices with ¹¹C-MET static imaging matrices will be conducted to assess correlation.

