7. PRIMARY STATISTICAL ANALYSES

7.1. Imaging Analyses

7.1.1. Overview of Planned Imaging Analyses

The imaging analyses will be based on the Safety population, unless otherwise specified.

Table 3 provides an overview of the planned imaging analyses, with full details of data displays being presented in Appendix 11: List of Data Displays.

Table 3 Overview of Planned Imaging Analyses

Endpoint / Parameter	Untransformed						
	Stats Analysis			Summary		Individual	
	T	F	L	T	F	F	L
¹⁸F-FDG PET/CT semi-quantitative parameters							
SUV _(mean/max/peak) , T/R Ratio, TIV				Yes ¹	Yes ¹	Yes ¹	Yes ¹
¹¹C-MET PET/CT semi-quantitative parameters							
SUV _(mean/max/peak) , T/R Ratio, TIV	Yes ³	Yes ³		Yes ²		Yes ²	Yes ²
Multiparametric MRI quantitative parameters							
K _{trans} ⁴ , ADC ⁴ , D ⁴ and f ⁴	Yes ³	Yes ³		Yes ²		Yes ²	Yes ²

NOTES:

- T = Table, F = Figure, L = Listing
- SUV = Standard Uptake Value, T/R Ratio = Tissue-to-reference ratio, TIV = Total Inflammatory Volume (TIV), K_{trans} = Exchange rate, ADC = Apparent Diffusion Coefficient, f = Microvascular volume fraction D = Pure Diffusion Coefficient
- Stats Analysis = Represents TFL related to any formal statistical analyses (i.e. modelling) conducted.
- Summary = Represents TFL related to any summaries (descriptive statistics) of the observed raw data.
- Individual = Represents FL related to any displays of individual subject observed raw data.
- 1: By region of interest (ROI)
- 2: By region of interest (ROI) and group (Healthy Volunteers (HV) or primary Sjogren's Syndrome (pSS) patient).
- 3: If data permits. Stats analysis for SUV_{mean/max/peak} for ¹¹C-MET PET/CT and K_{trans}, D and f for MRI.
- 4: Median and IQR (Interquartile Range) values for each parameter will be used.

7.1.1.1. ¹⁸F-FDG PET/CT

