7.1.2. Planned Imaging Statistical Analyses

Primary Statistical Analyses
Endpoint(s)

 • ¹¹C-MET PET/CT derived parameters, including but not limited to SUV_{peak}, SUV_{mean}, SUV_{max} • Multiparametric MRI derived parameters, including but not limited to (median and IQR) K_{trans}, (median and IQR) Pure diffusion coefficient (D), (median and IQR) microvascular volume fraction (f) and (median and IQR) ADC.
Model Specification

 • Parameters will be statistically analysed individually using an Analysis of Variance (ANOVA) model. • Terms fitted in the ANOVA model will include: Fixed categorical : Subject group (HV or pSS patient)
Model Checking & Diagnostics

 • Refer to Appendix 9: Model Checking and Diagnostics for Statistical Analyses : Model Checking and Diagnostics for Statistical Analyses.
Model Results Presentation

 • Estimates of Difference (pSS-HV) (or Ratio (pSS/HV) if log_e transformed) and 95% confidence interval for the derived parameters will be presented by ROI¹. • Plots of means (difference or ratio) and 95% confidence interval from the model will be generated for each ROI. • P-values will not be presented as formal hypothesis is not being tested. The interpretation will be based on point estimates and its precision (95% CI).

NOTES :

- [1]: When applicable for a given ROI, the analysis will be separated by the side of the ROI having higher parameter values and lower parameter values, and aggregated over both sides.

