11.12. Appendix 12: Example Mock Shells for Data Displays

Example : EFF_T1
 Protocol : 203818
 Population : Safety

Page 1 of n

Table 2.1
 Summary of ¹⁸F-FDG PET/CT parameters

Parameter: Parameter 1

Region of Interest	Sides	Group	N	n	Mean	SD	SE	Q1	Median	Q3	Min.	Max.
ROI 1	Low	pSS	xx	xx	xx.x	xx.xx	xx.xx	xx.x	xx.x	xx.x	xx	xx
		HV	xx	xx	xx.x	xx.xx	xx.xx	xx.x	xx.x	xx.x	xx	xx
	High	pSS	xx	xx	xx.x	xx.xx	xx.xx	xx.x	xx.x	xx.x	xx	xx
		HV	xx	xx	xx.x	xx.xx	xx.xx	xx.x	xx.x	xx.x	xx	xx
ROI 2	NA	pSS	Xx	Xx	xx.x	xx.xx	xx.xx	xx.x	xx.x	xx.x	xx	Xx
			xx	xx	xx.x	xx.x						

Note: NA: Sides are not applicable for all ROI.

Programming Note: Include Groups as a separate column next to Sides for 11C-MET PET/CT parameters summary.

Example : EFF_T2
Protocol : 203818
Population : Safety

Page 1 of n

Table X.X

Summary of Disease Activity (pSS only)

Disease Activity	N	n	Mean	SD	Median	Minimum	Maximum
------------------	---	---	------	----	--------	---------	---------

ESSDAI score

ESSRPI score

Patient Global assessment (VAS)

Physician Global Assessment (VAS)

Oral dryness numerical rating

Ocular dryness numerical rating

Example : EFF_T3
 Protocol : 203818
 Population : Safety

Page 1 of n

Table x.x

Summary of Correlation Between Disease Activity and Imaging Parameters

Disease Activity: [name of index]

Scan / Parameter	Side	Pearson's correlation / 95% CI	Spearman's correlation / 95% CI
¹¹ C-MET / SUVpeak	High	x.xx / (x.xx, x.xx)	x.xx / (x.xx, x.xx)
	Low	x.xx / (x.xx, x.xx)	x.xx / (x.xx, x.xx)
F-FDG / SUVpeak	High	x.xx / (x.xx, x.xx)	x.xx / (x.xx, x.xx)
	Low	x.xx / (x.xx, x.xx)	x.xx / (x.xx, x.xx)
MRI / Ktrans	High	x.xx / (x.xx, x.xx)	x.xx / (x.xx, x.xx)
	Low	x.xx / (x.xx, x.xx)	x.xx / (x.xx, x.xx)

Example: EFF_T4
Protocol: 203818
Population: Safety

Table x.xx

Point estimate and 95% CI for [imaging method] Derived Parameter of Difference in pSS vs. HV
95% CI for

ROI: [] Side: []

N	Group	n	Mean	Standard Error	Difference from HV	Difference (Lower, Upper)
xx	HV	xx	x.xx	x.xxx		
xx	pSS	xx	x.xx	x.xxx	x.xx	(x.xx, x.xx)
xx	HV	xx	x.xx	x.xxx		
xx	pSS	xx	x.xx	x.xxx	x.xx	(x.xx, x.xx)

Example: EFF_T5
 Protocol: 203818
 Population: Safety

Summary of the Posterior Distribution of the Ratio and Difference of Group Means for [Imaging method] parameters by Region

Parameter	ROI	Group	Prior Distribution for Θ	Value of σ used in the model	Posterior distribution					
					Mean	SD	Median	25th quartile	75th quartile	95% Credible Interval

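### If an FDG parameter needs transformation, the SAP swaps both the SE plot and the 95% CI plot for median +/- IQR, so the only planned FDG display with a confidence interval loses it

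*SAP*

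**What the plan says.** FDG SUV, tissue-to-reference ratio and TIV are primary endpoints (SAP 1 and 2.2), measured in pSS subjects only. Protocol 9.1 says that for FDG "summary statistics will be used to present each derived parameter". The SAP synopsis says that, in place of hypothesis tests, "an estimation and inference approach will be adopted to evaluate the objectives".

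The FDG displays are these:

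- **Figure 2.2**, mean +/- SE, and **Figure 2.3**, mean +/- 95% CI, by parameter and ROI. Both carry the note "Note: If transformation is required then use median +/- IQR".
- **Table 2.1**, "Summary of ¹⁸F-FDG PET/CT parameters". After N and n, the shell's statistics are "Mean SD SE Q1 Median Q3 Min. Max". There is no CI column.
- **Figures 2.1 and 2.4**, individual values and left/right ratios of SUVpeak.
- **Listing 26**, individual values.

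SAP Table 3 has no Stats Analysis entry for FDG. Its footnote ("3: If data permits. Stats analysis for SUV" and what follows) confines modelling to MET and MRI parameters.

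**The concern.** Two figures meant to show precision share a fallback that shows something else. SE and CI bars say how well the average is known and shrink as subjects are added. An IQR bar says how much subjects differ and settles to a constant. If the note is followed, Figure 2.3 drops its interval for precisely those parameters that were judged unsuitable for a raw-scale mean. Figure 2.2 then shows the same thing, unless the titles and contents are changed.

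The plan's only numerical support for its sample size is a precision figure, "calculated as half width of a 95% confidence interval for the mean" (Protocol 9.2, Table 5). The same table guides the decision to go from 8 to 12 pSS subjects (Protocol 9.2.2). A fallback that cannot show the effect of those extra subjects fits poorly with that reasoning.

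**Working it through.** **1. Is Figure 2.3 the only FDG interval?** The FDG displays listed above contain no other. Two other places might seem to supply one. The EFF_T3 shell gives 95% CIs for correlations that include FDG SUVpeak, but those are exploratory association intervals. Listings 28 and 29 name FDG model output, but they stand under the MET heading and no FDG model is planned, so they look mislabelled.

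**2. Reproduce the plan's own precision figures.** Half-width = t(0.975, n-1) x SD / sqrt(n). With SD = 1:

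- n = 8: 0.836 (Table 5: 0.84)
- n = 12: 0.635 (Table 5: 0.64)

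The t formula reproduces all 12 cells of Table 5. The normal quantile does not (0.57 at SD 1, N 12).

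**3. Compare bar widths, near-normal data.** The IQR is 2 x 0.6745 x SD = 1.349 SD.

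| | n = 8 | n = 12 |
|---|---|---|
| SE | 0.354 SD | 0.289 SD |
| 95% CI half-width | 0.836 SD | 0.635 SD |
| Literal reading (one IQR each side) / CI | 1.349/0.836 = 1.61 | 1.349/0.635 = 2.12 |
| Literal reading / SE bar | 3.82 | 4.67 |
| Q1 to Q3 reading / CI (full widths) | 1.349/1.672 = 0.81 | 1.349/1.271 = 1.06 |

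The ratios do not depend on the SD.

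**4. Put in the protocol's FDG figure.** Protocol 9.2 lists parotid SUVmax in pSS as mean 2.75, SD 0.61 (n=32). A log-normal shape is assumed here, since the note applies only after transformation. CV = 0.61/2.75 = 0.222; SD of the logs = sqrt(ln(1 + 0.222^2)) = 0.219; geometric mean = 2.75/sqrt(1 + 0.222^2) = 2.685.

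- Back-transformed 95% CI: 2.235 to 3.225 at n = 8; 2.336 to 3.086 at n = 12.
- Literal median +/- IQR: 1.888 to 3.481 at either n. This covers about 83% of individual values.
- Q1 to Q3: 2.316 to 3.112 at either n, almost coinciding with the CI at n = 12.

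**5. Does the bar respond to sample size?** In 100,000 simulated samples from that log-normal, the mean full width of literal median +/- IQR was 1.34, 1.42 and 1.55 at n = 8, 12 and 48. The geometric-mean CI width fell from 0.96 to 0.74 to 0.34. Sample quartiles computed by linear interpolation understate the IQR a little in small samples, so the simulated ratios are 1.34/0.96 = 1.4 at n = 8 and 1.42/0.74 = 1.9 at n = 12, somewhat below those in step 3.

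**The case against.** The note is conditional and acts on displays only. Appendix 9 sets distribution checks for the ANOVA and the correlations and gives no trigger for FDG summaries, so the fallback may never be used. No estimate or decision rule changes. The protocol promised only summary statistics for FDG, and Protocol 9.4.1 lists between-subject variability among the things to examine, which a spread display serves. All of this stands and limits the weight of the point. It does not make an IQR a fair substitute in a figure specified as a 95% CI.

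Four stronger readings are tempting, and the documents do not support them:

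- **That precision is lost altogether.** Table 2.1 keeps SE and n, and Listing 26 gives the values, so a reader could build an interval. The reported SE, though, is on the scale judged unsuitable.
- **That the bars would reach impossible negative values.** This needs the literal reading and a log-normal CV of about 80% or more. The protocol's FDG CVs are 0.61/2.75 = 22%, 0.53/1.80 = 29% and 0.68/1.90 = 36%. Even at 36% the lower end is 0.943/1.789 = 0.53 times the median, and quartiles of a positive variable cannot be negative.
- **That the SAP requires FDG to be read through CIs.** The sentence "The interpretation will be based on point estimates and its precision (95% CI" (SAP 7.1.2) belongs to the ANOVA of MET and MRI.
- **That MET and MRI already solve the same problem.** Their ratio with 95% CI is a pSS-to-healthy contrast, which FDG cannot have. The closest analogues, Figures 2.6 and 2.11, have no transformation rule.

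Finally, the phrase is often loose shorthand for the median with its quartiles. That is a fair reading, so the size of the discrepancy is given for both.

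**Conclusion.** The point holds, conditionally and at modest weight. If an FDG parameter is judged to need transformation, a stated rule removes the only planned 95% CI for a primary FDG parameter and puts between-subject spread in its place, in two figures that become identical. The literal bars are about 1.6 times (n=8) and 2.1 times (n=12) the CI width, taking the normal-theory IQR and the t-interval behind Table 5; the quartile bars are about 0.8 and 1.06 times. The quartile reading is the less conspicuous hazard, because at n=12 it looks like a CI. How often the rule would apply is unknown, because no FDG trigger is given. In an exploratory pilot this should be corrected, but no study conclusion turns on it.

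**What to change.** Replace the note on both figures.

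- **Figure 2.3:** when log transformation is needed, plot the geometric mean with its back-transformed 95% t-interval. For parameters that can be zero, plot the median with an order-statistic 95% CI. TIV is assumed to be one, since there may be no inflamed volume; the documents do not say. At n=12 the 3rd to 10th ordered values give 1 - 2(1+12+66)/4096 = 96.1%. At n=8 the 2nd to 7th give only 1 - 2(1+8)/256 = 93.0%, so the minimum to maximum (1 - 2/256 = 99.2%) is needed; report the actual coverage.
- **Figure 2.2:** plot the geometric mean with back-transformed +/- 1 SE, or the median with Q1 to Q3 labelled as between-subject spread.
- **Titles:** make each title match what is plotted.
- **Table 2.1:** footnote the matching geometric mean (or median) and 95% CI for FDG only, because the EFF_T1 shell also serves the MET and MRI summaries.

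The cost is one revised programming note on two figures, a title change where the fallback applies, and one FDG footnote. No new data or change to study conduct is needed.

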11.11.7. Pharmacokinetic Tables

Pharmacokinetic: Tables					
No.	Population	IDSL / TST ID / Example Shell	Title	Programming Notes	Deliverable [Priority]
Radioactivity concentrations (static ¹⁸F-FDG and ¹¹C-MET)					
3.1.	PK	PKCT1	Summary of ¹¹ C-MET Tracer Pharmacokinetic Concentration Data	Paginated by Group and type of blood (Whole and Plasma). Group to include pSS, HV and overall. Subheading: 'Subject group: [group]' 'Blood: [blood type]'	SAC
Radiopharmacokinetic parameters					
3.2.	PK	PKPT1	Summary of Radiopharmacokinetic Parameter – Influx Rate Constant (K _i) from ¹¹ C-MET PET/CT	Paginated by Group Group to include pSS, HV and overall. Subheading: 'Subject group: [Group]'	SAC
3.3.	PK	EFF_T3	Summary of correlation between PK modelling index with ¹¹ C-MET PET/CT static imaging parameters	Paginated by Group Group to include pSS, HV and overall. Subheading: 'Subject group: [Group]' Change last three column titles to 'SUVpeak' 'SUVmean' and 'SUVmax' respectively. Footnote: Parotid gland side with the highest and lowest uptake values.	SAC

11.11.8. Pharmacokinetic Figures

Pharmacokinetic : Figures					
No.	Population	IDSL / TST ID / Example Shell	Title	Programming Notes	Deliverable [Priority]
Radioactivity concentrations (static ¹⁸ F-FDG and ¹¹ C-MET)					
3.1.	PK	PKCF1P	Plot of Individual ¹¹ C-MET Tracer Pharmacokinetic Concentration-Time (Linear and Semi-Log)	Paginated by Group and type of blood (Whole and Plasma). Group to include pSS, and HV. Subheading: 'Subject group: [group]' Blood: [blood type]	SAC
Radiopharmacokinetic parameters					
3.2.	PK	EFF_F4	Plot of Individual Radiopharmacokinetic Parameter Influx Rate Constant (K _i) versus Standardised Uptake Value of ¹¹ C-MET PET/CT	Paginate by parameters SUVpeak, SUVmean and SUVmax ROI: Parotid Gland Plot Ki along X axis and SUV parameter value along Y axis. Colour by subject group. Panel by sides – side with higher parameter values and side with lower parameter values. Include Pearson's product moment correlation	SAC

